
5 STUDY OBJECTIVES

5.1 PRIMARY

To compare the effect of Praluent® with SoC on coronary atheroma progression (percent change in normalized TAV) after 9 months of treatment in patients who had ACS within 4 weeks prior to randomization, with hypercholesterolemia treated with any statin.

5.2 SECONDARY

- To compare the effect of Praluent® with SoC on secondary endpoints including absolute change in PAV and normalized TAV after 9 months of treatment.
- To evaluate the effect of Praluent® on LDL-C, Apo B, TGs, non-HDL-C and Lp(a) after 9 months treatment.
- To evaluate the safety of Praluent® including the occurrence of CV events (CHD death, non-fatal MI, fatal and non-fatal ischemic stroke, unstable angina requiring hospitalization) throughout the study.

6 STUDY DESIGN

This is a phase 4, open-label, 1:1 randomized, blinded IVUS analysis, parallel group, multicenter study to investigate the effect of alirocumab on coronary atheroma volume in Japanese patients with hypercholesterolemia, who have recently suffered from ACS and are failing to reach the recommended LDL-C levels as defined by JAS guidelines for very high CV disease risk in spite of stable statin therapy. Randomization will be stratified by 'on statin therapy' or 'not on statin' therapy at the time of ACS onset. As a phase 4 study, the dose regimen is in line with the approved regimen in Japan; starting dose is 75 mg Q2W with up-titration to 150 mg Q2W if patients do not reach their target LDL-C level.

Approximately 200 patients from approximately 40 study sites will be enrolled and randomized with a treatment period of 9 months. Patients who suffer ACS events despite stable statin therapy and whose LDL-C is ≥ 100 mg/dL will be enrolled. If patients are not on any statin therapy at the time of ACS onset, they will start either atorvastatin 10 mg/day or rosuvastatin 5 mg/day immediately after the ACS diagnosis, and the patients whose LDL-C is not adequately controlled with statin (in principle, LDL-C target level ≥ 100 mg/dL, but this may not apply if the responsible physician considers LDL-C level inadequate on statin. Patients who have LDL-C < 70 mg/dL cannot be enrolled) at 2 to 4 weeks after the ACS diagnosis will be also enrolled.

6.1 DESCRIPTION OF THE STUDY

The study consists of a 36-week open-label treatment period started within 4 weeks after ACS diagnosis and appropriate percutaneous coronary intervention (PCI) with bare metal stent (BMS) or drug eluting stent (DES) placement and includes post-treatment IVUS imaging (evaluation IVUS imaging, Week 36 [end of treatment (EOT)] ± 2 weeks). The patient who did not receive PCI but has undergone coronary artery bypass graft surgery or received medical therapy only can be included if the analyzable IVUS imaging is obtained.

A 36-week open label treatment period: Patients will be randomized to either alirocumab arm or SoC arm. Randomization will be stratified by on statin therapy or not on statin therapy at the ACS onset. While the last Praluent® administration will be performed at Week 34, evaluation IVUS imaging can be carried out between Week 34 and Week 38 (Week 36 ± 2 weeks) considering potential scheduling difficulty. The Investigator/sub-Investigator is to make their best effort to schedule the evaluation IVUS imaging within this time period. If a patient cannot undergo evaluation IVUS by Week 36, the last Praluent® administration will be performed at Week 36 and the Investigator/sub-Investigator will make their best effort to carry out evaluation IVUS before Week 38 while maintaining sufficient alirocumab effect at the evaluation IVUS imaging (see [Section 1.2](#)). Patients in the SoC arm will continue the study treatment until evaluation IVUS.

- Alirocumab arm: Praluent® 75 mg Q2W on top of statin therapy (atorvastatin ≥ 10 mg/day or rosuvastatin ≥ 5 mg/day within the range of statin doses approved by the Health Authority) will be administered.

Note: At Week 14, patients whose LDL-C level measured at Week 12 by central laboratory remains ≥ 100 mg/dL in spite of 75 mg Praluent® administration, will receive Praluent® dose up-titrated to 150 mg Q2W.

Note: Patients can choose self-injection of Praluent® (alirocumab) at home any time, if they wish self-injection at home and the Investigator/sub-Investigator considers it feasible.

Before starting self-injection at home, the Investigator/sub-Investigator must explain to the patients using the operation procedure for administration of IMP. If necessary, patients can use the training kits. Patients are allowed to perform self-injection at home if they successfully perform the correct self-injection of Praluent® under direct supervision of site medical staff at the study site once, and the Investigator/sub-Investigator considers that they can perform self-injection at home correctly. They can use tools to assist.

Regardless of the timing when the self-injection is started, patients must visit the study site at least every 4 weeks, and at Week 0, Week 4, Week 12, Week 14, Week 24 and Week 36.

Patients must record self-injection at home in the diary. At each visit, they must bring the diary, and the site medical staff must check their records.

If self-injection at home is performed, IMPs will be provided for only number of times of self-injections at home until the next visit. Patients must return used and unused IMPs to the site medical staff at the next visit.

Patients can discontinue self-injection at home any time. The Investigator/sub-Investigator must have patients discontinue self-injection at home, if the Investigator/sub-Investigator judges that the patients are not able to perform self-injection at home correctly. Patients who discontinue self-injection at home can have injections performed by medical staff at the study site.

- *SoC arm: Statin (atorvastatin ≥ 10 mg/day or rosuvastatin ≥ 5 mg/day) and non-statin LMTs will be continued at the same doses determined after ACS diagnosis and PCI unless modifications are considered necessary by Investigator/sub-Investigator. The target LDL-C level is set as <100 mg/dL.*

Note: 1) Stable dose statin therapy (atorvastatin ≥ 10 mg/day or rosuvastatin ≥ 5 mg/day within the range of statin doses approved by the Health Authority) will be administered, and the dose will be adjusted to achieve the LDL-C target level <100 mg/dL; 2) Concomitant non-statin LMTs will be considered if LDL-C target level <100 mg/dL cannot be achieved with statin monotherapy. Adjustment of LMTs is to be performed based on, but not limited to, the above rule.

The evaluation IVUS imaging will be performed at the EOT (Week 36 \pm 2 weeks). The detailed instructions of IVUS imaging procedure and the image data processing are described in the specific manual. This manual also includes detailed IVUS imaging procedures and image processing at the initial IVUS imaging performed at the time of PCI for ACS.

Note: If the study site is able to perform optical coherence tomography (OCT) at the time of the IVUS imaging, OCT will be performed as a substudy. The OCT will be performed following the OCT substudy protocol.

6.2 DURATION OF STUDY PARTICIPATION

6.2.1 Duration of study participation for each patient

The study consists of a 36-week open-label treatment period including the evaluation IVUS imaging (Week 36 ± 2 weeks) starting within 4 weeks after ACS diagnosis and appropriate PCI. The evaluation IVUS imaging is allowed to be performed between Week 34 and Week 38 depending on the Investigators/sub-Investigators' decision (36 weeks [EOT] ± 2 weeks). Therefore, the study period per patient will be up to 38 weeks.

Patients who experience ongoing SAE or adverse event of special interest (AESI) at the pre-specified study end-date should be followed until resolution, stabilization, or death, and related data will be collected. The end of study per patient is the last protocol planned visit or the resolution/stabilization of all SAEs or AESIs, whichever comes last.

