10.1.1.1.4 Study Site Visit 4 (Week 24 / D169 ± 7 days)

This visit includes:

- On-site visit.
- EQ-5D patient questionnaire.
- IMP/NIMP compliance check including diet therapy (Patients should be on a diet following JAS guideline or equivalent).
- Body weight.
- Vital signs: heart rate and sitting SBP and DBP.
- Record of all concomitant medications including CV medications.
- Collection of adverse events including CV events (if any).
- Fasting blood sample listed below will be collected and measured.
 - Hematology and chemistry.
 - TC, calculated and directly measured LDL-C, HDL-C, TG, non-HDL-C (central laboratory).
 - HbA1c (central laboratory).

Note: Additional blood samples can be obtained for measurement of above listed items and others at the study site by Investigator's judgment as needed.

- When the Investigator or the site medical staff confirms all required measurements are completed, the patient in the alirocumab arm will receive Praluent® administration.
- The patient should be observed for at least 30 minutes after Praluent® administration.
- If patient is in the SoC arm, ongoing LMTs will be continued unless modification of LMTs is made by the Investigator's medical judgment.
- For the patient in the alirocumab arm, an appointment will be given for next Praluent® administration visit (Week 26 / D183).
- For the patient in the SoC arm, an appointment will be given for next phone-call interview (Week 28 / D197).
- The Investigator should make a schedule with the patient for the evaluation IVUS study at the EOT (Week 36 ± 2 weeks) by this on-site study visit if possible.

10.1.1.1.5 Study Site Visit 5 (End of Treatment Visit, Week 36 / D253 ± 14 days)

This study visit includes:

- On-site visit.

- Contact the registration center to document the end of study.

Note: If the evaluation IVUS imaging is completed in this visit, EOT will be the end of study. If the evaluation IVUS imaging is scheduled after this visit, the contact with the registration center will be made when the evaluation IVUS imaging has been completed and this point is considered the end of study.

- EQ-5D patient questionnaire.
- IMP/NIMP compliance check including diet therapy (Patients should be on a diet following JAS guideline or equivalent).
- Body weight.
- Vital signs: heart rate and sitting SBP and DBP.
- Record of all concomitant medications including CV medications.
- Collection of adverse events including CV events (if any).
- Urine pregnancy tests (WOCBP).

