10.4.2 General guidelines for reporting adverse events

All AEs, regardless of seriousness or relationship to study treatment, spanning from the signature of the informed consent form until the end of the study as defined by the protocol for that patient, are to be recorded on the corresponding page(s) or screen(s) of the e-CRF.

Whenever possible, diagnosis or single syndrome should be reported instead of symptoms. The Investigator/sub-Investigator should specify the date of onset, intensity, action taken with respect to study treatment, corrective treatment/therapy given, additional investigations performed, outcome, and his/her opinion as to whether there is a reasonable possibility that the AE was caused by the study treatment or by the study procedure(s).

The Investigator/sub-Investigator should take appropriate measures to follow all AEs until clinical recovery is complete and laboratory results have returned to normal, or until progression has been stabilized, or until death, in order to ensure the safety of the patients. This may imply that observations will continue beyond the last planned visit per protocol, and that additional investigations may be requested by the monitoring team up to as noticed by the Sponsor. When treatment is prematurely discontinued, the patient's observations will continue until the end of the study as defined by the protocol for that patient.

Laboratory and vital signs are recorded as AEs only if:

- Symptomatic and/or
- Requiring either corrective treatment or consultation, and/or
- Leading to study treatment discontinuation or modification of dosing, and/or
- Fulfilling a seriousness criterion, and/or
- Defined as an AESI

See [Section 17](#), Appendix F for summary of AE reporting guidelines.

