11.4.3 Analyses of safety data

The summary of safety results will be presented by treatment arm. No formal inferential testing will be performed. Summaries will be descriptive in nature.

Observation period

The observation period of safety data will be as follows:

- **Pre-treatment period** is defined as the time from the signed informed consent date up to the day of randomization.
- **TEAE period** is defined as the time from the day of randomization up to the last administration + 14 days (+ 7 days), or end of study, whichever comes first.
- **Post-treatment period** is defined as the time starting the day after the end of the TEAE period up to the end of the study (see definition in [Section 6.2.1](#)).
- **On-study observation period** is defined as the time from the day of randomization up to the end of the study (see definition in [Section 6.2.1](#)).

All safety analyses will be performed on the safety population using the following common rules:

- The potentially clinically significant abnormality (PCSA) values are defined as abnormal values considered medically important by the Sponsor according to predefined

criteria/thresholds based on literature review and defined by the Sponsor for clinical laboratory tests and vital signs.

- PCSA criteria will be determined which patients had at least 1 PCSA during the TEAE period, taking into account all evaluations performed during the TEAE period, including unscheduled or repeated evaluations. The number of all such patients will be the numerator for the PCSA percentage.

Drug-induced liver injury

The liver function tests, namely ALT, AST, alkaline phosphatase, and total bilirubin, are used to assess possible drug-induced liver toxicity. The proportion of patients with PCSA values at any post-baseline visit by baseline status will be displayed by treatment arm for each parameter.

A graph of distribution of peak values of ALT versus peak values of total bilirubin will also be presented. Note that the ALT and total bilirubin values are presented on a logarithmic scale. The graph will be divided into 4 quadrants with a vertical line corresponding to $3 \times \text{ULN}$ for ALT and a horizontal line corresponding to $2 \times \text{ULN}$ for total bilirubin.

The incidence of liver-related AEs will be summarized by treatment arm. The selection of preferred terms will be based on standardized MedDRA query (SMQ) "Hepatic disorder."

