#### **2.1.4.2 Deaths**

The deaths observation periods are per the observation periods defined above.

- Death on-study: deaths occurring during the on-study observation period
- Death on-treatment: deaths occurring during the TEAE period
- Death post-study: deaths occurring after the end of the study

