#### ***Analysis of pre-treatment and post-treatment adverse events***

- All pre-treatment adverse events by primary SOC and PT sorted by the internationally agreed SOC order and decreasing incidence of PTs within each SOC;
- All pre-treatment adverse events leading to treatment discontinuation (if any) by primary SOC and PT, sorted by the internationally agreed SOC order and decreasing incidence of PTs within each SOC;

- All post-treatment adverse events by primary SOC and PT, sorted by the internationally agreed SOC order and decreasing incidence of PTs within each SOC;
- All post-treatment SAEs by primary SOC and PT, sorted by the internationally agreed SOC order and decreasing incidence of PTs within each SOC.

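### The period for counting post-treatment adverse events and on-study deaths depends on whether the patient has an open SAE or AESI, and the end-of-study definitions conflict

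*Protocol*

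**What the plan says.** **Per-patient end of study.** Protocol 6.2.1: "The end of study per patient is the last protocol planned visit or the resolution/stabilization of all SAEs or AESIs, whichever comes last". The same section says "the study period per patient will be up to 38 weeks", and that patients with an ongoing SAE or AESI "should be followed until resolution, stabilization, or death, and related data will be collected". The Visit 5 note in 10.1.1.1.5 differs: "If the evaluation IVUS imaging is completed in this visit, EOT will be the end of study"; if the imaging comes later, its completion is the end of study.

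**What is recorded to that date.** Protocol 10.4.2 covers all adverse events, "spanning from the signature of the informed consent form until the end of the study as defined by the protocol for that patient".

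**What is counted to that date.** Protocol 11.4.3 ends the post-treatment period at the end of the study, and its on-study period "is defined as the time from the day of randomization up to the end of the study". Both refer to 6.2.1. The TEAE period stops at the earlier of last administration plus 21 days and end of study. SAP 2.1.4 repeats these periods for both arms without defining end of study.

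**Tables.** SAP 2.4.5.1 plans "All post-treatment adverse events by primary SOC and PT, sorted by the internationally agreed SOC order", and the same for SAEs. SAP 2.1.4.2 has "Death on-study: deaths occurring during the on-study observation period", with a separate category for deaths after the end of the study.

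**The concern.** If the end of counting is set by whether an event is still open, patients who are already ill stay under observation for new events while others leave. The by-arm tables of post-treatment events and on-study deaths use the number of patients as denominator, so they do not compare equal observation time. A difference could appear between arms with identical risk, or a real one could be blurred. The conflicting definitions also mean that two programmers working from the same documents could produce different tables.

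**Working it through.** **The plan's own figure.** The upper limit of 38 weeks is Day 38 × 7 + 1 = 267, which is Day 253 (Week 36) + 14. It agrees with the IVUS window and the Visit 5 note. It does not agree with the uncapped rule in 6.2.1.

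**Inputs.** The last alirocumab dose is at Week 34 (Day 239), or at Week 36 (Day 253) if the IVUS is late. SoC treatment continues to the IVUS (protocol 6.1). The planned last visit is Day 253. The 60-day extension below is an assumption for illustration.

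**Formulas.** E = planned last visit + days an SAE/AESI stays open after it. TEAE end = min(last administration + 21, E). The post-treatment period runs from TEAE end + 1 to E.

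| Patient | TEAE end | Post-treatment days | On-study end |
|---|---|---|---|
| Alirocumab, nothing open | min(260, 253) = 253 | 0 | 253 |
| Alirocumab, open 60 days | min(260, 313) = 260 | 313 − 260 = 53 | 313 |
| SoC, nothing open | min(274, 253) = 253 | 0 | 253 |
| SoC, open 60 days | min(274, 313) = 274 | 313 − 274 = 39 | 313 |

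- The TEAE gain is at most 260 − 253 = 7 days on alirocumab and 274 − 253 = 21 days on SoC. With a Week 36 dose or SoC treatment to Week 38, and IVUS at Day 267, the gains are again 274 − 267 = 7 and 288 − 267 = 21.
- A patient who stops treatment at Day 85 but stays to Week 36 has TEAE end 85 + 21 = Day 106 either way. Early stoppers therefore have post-treatment time without an open event; completers on schedule do not.
- A death on Day 300 is on-study if an event is open until Day 313, and post-study if none is open.

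**Direction between arms.** Take the alirocumab TEAE figure from the Japanese phase 3 study in protocol section 4 (90.9% over 52 weeks) and assume a constant rate in both arms: −ln(1 − 0.909)/52 = 0.0461 per week. Assume events stay open 8 weeks. Post-treatment time is then 8 − 1 = 7 weeks on alirocumab and 8 − 3 = 5 weeks on SoC. The chance of a new event is 1 − exp(−0.0461 × 7) = 0.276 and 1 − exp(−0.0461 × 5) = 0.206. Multiplying by the share of patients with an open event, which the documents do not give:

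| Share open, alirocumab / SoC | With a post-treatment AE from the extension |
|---|---|
| 10% / 5% | 2.8% vs 1.0% |
| 10% / 10% | 2.8% vs 2.1% |
| 5% / 10% | 1.4% vs 2.1% |

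The sign follows the assumed shares. In that phase 3 study the two triggers pointed in opposite directions: serious TEAEs in 7.0% on alirocumab and 12.5% on placebo, and treatment-related injection site reactions in 12.6% and 4.2%.

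**CV events.** The four statements of the window differ:
- protocol 9.2.1: consent to end of study;
- protocol 10.6.3: randomization to the end-of-study visit;
- SAP 2.1.4.1: randomization to a follow-up visit that the schedule does not contain;
- SAP 2.4.5.1: treatment-emergent events only.

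For scale under 9.2.1, use the 10% one-year rate in protocol section 4 as a constant hazard, λ = −ln(0.90)/365.25 per day. The expected count is 100 × (1 − exp(−252λ)) = 7.0 per 100 over 36 weeks. With share q open, L extra days and hazard multiple h, the extra count is 100 × q × (1 − exp(−λhL)). It runs from 0.04 (q = 5%, L = 30, h = 1) to 2.4 (q = 20%, L = 90, h = 5). The ranges for q, L and h are assumptions.

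**The case against.** The best defence is that the main safety analysis is largely protected. SAP 2.4.5.1 puts the focus on TEAEs, caps them at 21 days after last administration, and also reports their frequency over time per patient-month. Protocol 11.4.3 rules out formal testing of safety. This stands and limits the consequence, but for completers on schedule the end of study, not the 21 days, closes the TEAE window, so that window is not fully insulated.

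Section 6.2.1 speaks only of collecting data related to the ongoing event. On that reading, new unrelated events would not be captured during the extension. Section 10.4.2 says otherwise, and the documents do not settle it.

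Deaths after the end of study are not lost, because a post-study category is planned. They change category, and that category still depends on whether an event was open.

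Three stronger readings are tempting and are not supported:
- A reader might infer that the rule inflates alirocumab counts through AESIs specific to that drug. Injection site reactions do need the injection. Most AESIs, such as ALT elevation or allergic, neurologic and muscle events, can occur in either arm, and protocol 10.4.4.1 includes symptomatic overdose with non-investigational products. The TEAE gain is larger on SoC.
- A reader might infer that the planned CV table runs to the extended date. The SAP summarizes treatment-emergent CV events only, so that table is affected only through the TEAE cap.
- A reader might treat a by-arm percentage such as 2.8% versus 1.0% as the expected bias. It rests on shares and durations that are not in the documents.

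**Conclusion.** The point holds for post-treatment AEs and SAEs and for the on-study classification of deaths: their counting time depends on the outcome and has no upper limit in 6.2.1. For TEAEs the effect is small and bounded, at 7 days (alirocumab) or 21 days (SoC), and arises only in patients with an open event. These bounds assume treatment and visits on schedule. The size of the effect on the tables depends on how many events are open at Week 36 and for how long, which the documents do not give. Its direction between arms cannot be predicted.

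The definitions also need reconciling whatever the size: 6.2.1 against itself and 10.4.2, the Visit 5 note, the undefined term in the SAP, and the four CV windows. In addition, protocol 9.2.1 cites 6.2.2, the whole-trial end, for the per-patient definition found in 6.2.1. The primary and key secondary endpoints, the sample size and alpha are not touched. This is a worthwhile correction to descriptive safety tables.

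**What to change.** For analysis only, define one cut-off date by a rule that ignores events: the last planned visit including the evaluation IVUS, or a fixed number of days after it for everyone. End the TEAE cap, the post-treatment period and the on-study period there. Use the same definition in protocol 6.2.1, 10.1.1.1.5 and 11.4.3 and in SAP 2.1.4. Correct the reference to 6.2.2 in protocol 9.2.1, and reconcile the CV windows in protocol 9.2.1 and 10.6.3 and SAP 2.1.4.1 and 2.4.5.1.

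Leave collection, reporting and follow-up of open SAEs and AESIs as they are. List new adverse events after the cut-off separately, and keep later deaths in the existing post-study row.

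The cost is protocol and SAP wording. A few late events move from the by-arm tables to a listing or to the post-study category. With the last-planned-visit option no extra data are needed; a fixed period after it would need contact with every patient to its end.
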